## Sensitivity analyses

- As sensitivity analyses, the treatment groups will be compared by **modified intention-to-treat (mITT)** after excluding participants who did not receive any of the assigned investigational agent (active or control). This mITT analysis will be provided at important decision points, e.g., when the test statistic approaches the monitoring boundary, and for the final analyses after completion of the trial.
- Treatment groups will be compared for the pulmonary and pulmonary+ outcomes on Days 1-7, to monitor the consistency of the treatment effect over time.

## Assessment of model assumptions

- For the pulmonary and pulmonary+ outcomes at Day 5, the proportionality assumption of the odds ratio will be assessed (by including the interaction between the treatment group indicator and indicators for the Day 5 cumulative ordinal categories in the model, as well as the interactions between the treatment group indicator and the indicators for the strata by baseline pulmonary+ categories and site pharmacy; this corresponds to testing for separate slopes using a partial proportional odds model, see section 3 under “ordered categories”). If there is evidence for non-proportionality, the summary odds ratio in the proportional odds model will still be used to quantify the treatment effect, and the analyses of the dichotomized ordinal outcome categories will be used to help interpret the treatment effect.
- The sample size of 300 (150 per study arm) is sufficient to detect a summary OR of 1.60 for the comparison of the investigational agent versus control for each of the two ordinal outcomes with 95% power. The power of the tests depends on the hypothesized OR and the hypothesized distribution in the control group used for the sample size calculations. At the time of the early futility review, the deviation of the observed distribution from the hypothesized distribution in the control arm will be assessed, and the impact on the power of the trial will be estimated.

## 10.3 Interim Monitoring Guidelines for the Primary Endpoint

This section describes the interim monitoring guidelines that apply after the investigational agent has passed the initial futility assessment (after approximately 150 participants per study arm are enrolled).

As a guideline, asymmetric boundaries will be provided to monitor the primary endpoint (time to sustained recovery) for overwhelming benefit or for harm. The trial of an investigational agent should be stopped for efficacy only if there is clear and convincing evidence of superiority

of the agent versus the pooled control group with respect to the primary outcome, time to sustained recovery. For monitoring superiority, the Lan-DeMets spending function analogue of the O'Brien-Fleming boundaries will be used, with a 1-sided 0.025 level of significance over multiple looks. For computing the Lan-DeMets boundary, the information fraction at each interim analysis will be the observed total number of sustained recoveries divided by the planned number of sustained recoveries (N=843).

The monitoring boundary for harm is asymmetric, requiring less evidence to stop for harm than for superiority; a Haybittle-Peto boundary with 2.5 SD for the first 50 participants enrolled and 2.0 SD afterwards will be used as a guideline for harm. With this approach, less evidence will be required for crossing a boundary for harm than for benefit.

At each full interim review after the first 169 participants have achieved sustained recovery (20% information time), the following will be provided:

- Signed square root of the value of the test statistic for Gray's test with  $\rho=0$ , ("Z-value") comparing the investigational agent versus the control group for the primary endpoint through Day 90, plotted over information time, and the asymmetric monitoring boundaries: the O'Brien-Fleming boundary with Lan-DeMets  $\alpha$ -spending function for superiority (one-sided test with  $\alpha=0.025$ ), and the asymmetric, Haybittle-Peto boundary for harm described above.
  - **Comment:** Test statistics for the primary treatment comparison will be coded such that the value of the test statistic  $> 0$  favors the investigational agent. Thus, in case of harm, the Haybittle-Peto boundary with 2 SD of the normalized test statistic, is crossed if the Z-value for the test statistic is below -2, irrespective of information time.

In addition to the current value of the test statistic, the corresponding values of the test statistic at the previous reviews will be plotted over information time, (1) as presented at the previous DSMB meetings, and (2) re-calculated with current data (using the cut-dates of the previous reports).

- History of the estimated rate ratios for time to sustained recovery with 95% CIs and p-values (by Fine-Gray's method), and normalized test statistic values and p-values for Gray's test at previous DSMB reviews, as presented, and recalculated with the current data (using the cut-date of the previous reports). The latter provides information on the influence of a possible time lag in the ascertainment of sustained recovery.

## 10.4 Interim Monitoring for Futility

After investigational agents have passed the initial futility assessment (based on the pulmonary and pulmonary+ outcomes at Day 5, assessed for the first 300 participants), further futility analyses will be based on the primary outcome of *time to sustained recovery*. The aim of these analyses will be to consider whether an investigational agent should be discontinued due to a low probability of achieving statistical significance for the primary endpoint of sustained recovery at the completion of the 90 day follow-up.

Conditional power calculations for time to sustained recovery will be presented under a range of scenarios. In the primary futility analysis, it will be assumed that the treatment effect for the

future, as yet unobserved follow-up will be as hypothesized in the study design (RRR=1.25). As secondary analysis, the treatment effect for future follow-up will be assumed to be similar to the observed effect. Additional scenarios may be provided. Typical futility guidelines recommend stopping a trial when conditional power (assuming the originally hypothesized treatment effect for the future follow-up) is below 10%-15%.

As a guideline, futility will first be assessed when 50% of the planned number of sustained recoveries have occurred, and a value of 15% will be suggested as a threshold for the conditional power. An additional assessment will take place at 75% of the events. Conditional power will be computed using Gray's test with  $p=0$ , the competing risk analogue of the log-rank test.

Decisions to terminate an agent for futility will include a broad assessment of the risk/benefit trade-off in addition to these guidelines.

## 11 Data Completeness and Study Conduct

According to the protocol, the pulmonary and pulmonary+ outcomes will be assessed on days 0-7; the decision rules for the initial futility assessment are based on these outcomes on Day 5. The pulmonary outcome will also be assessed on Days 14 and 28. The primary outcome, "time to sustained recovery", will be assessed through Day 90. Clinical data will be collected on Days 0-7, 14, 28, 60 and 90; mortality and re-hospitalizations will be assessed through 18 months. After hospital discharge, in-person visits are scheduled on Days 1, 3, 5, 28, and 90, when blood is collected (plasma and serum); other visits may be conducted by phone (Days 7, 14, 42, 60, and 75). The data collection schedule is included in [Appendix D](#) of this SAP.

Data completeness and study conduct reports will be provided by treatment group (for the closed report) and pooled across treatment groups (for the open report). Data summaries for the infusion of the investigational agent on Day 0 are described in [Section 6](#); several of those reports are also relevant for monitoring study conduct and will be included in the open report or provided to study leadership, pooled across treatment groups.

The following data summaries will be provided to assess data completeness and study conduct:

- Number and percent of participants with protocol deviations, and type of protocol deviation
- Expected and observed number (% of expected) of participants who completed visits on Days 1-7, 14, 28, 42, 60, 75, and 90.
- Expected and observed number (% of expected) of participants with known outcome status for the pulmonary and the pulmonary+ outcomes on Day 5.
- Ascertainment of the primary outcome: Expected and observed number (% of expected) of participants with known status of "time to sustained recovery" at days 28, 60, and 90. To ascertain "sustained recovery", several elements are required: vital status; the status of hospitalization; if discharged, the status of the residence ("home" versus other).
- Expected and observed number (% of expected) of participants with known vital status at days 5, 14, 28, 60 and 90, and at months 6, 12, and 18.

- Number and percent of participants who withdrew consent or were lost to follow-up (no contact and unknown vital status for 45+ days).
- If substantial numbers of participants are lost to follow-up (e.g., more than 10% of participants), Kaplan-Meier estimates for the cumulative proportion of participants who are lost to follow-up over time, by treatment group, will be provided (closed report only).
- Listing of participants who withdrew consent, including dates of randomization, pulmonary+ category at baseline, receipt of study treatment, date of withdrawal, and reason of withdrawal.
- Length of follow-up: Median, IQR, range
- Collection of specimens: Expected and observed number (% of expected) of participants with specimens collected as specified by the protocol, by visit.
- Expected and observed numbers of participants with local laboratory data at baseline and on Day 5.

A visit counts as “expected” if the visit window has closed or the data have been received.

## 12 SARS-CoV-2 Antibody, Antigen, and Viral RNA Levels

SARS-CoV-2 neutralizing antibody (nAb) levels, anti-N antibody levels, and plasma antigen levels are measured in stored plasma specimens collected at baseline (Day 0), Day 1, Day 3, and Day 5. SARS-CoV-2 RNA levels are determined from mid-turbinate nasal swabs, collected at baseline. Assays are described in [Appendix F](#).

The statistical analyses described in this section are based on the analysis plan for antibody and antigen data for bamlanivimab (LY-CoV555), the *Addendum to Statistical Analysis Plan (Version 1.0) Therapeutics for Inpatients with COVID-19 (TICO) ACTIV-3 INSIGHT 014*, dated 14 April 2021. The current update to the SAP is further informed by the completed analyses of antibody, antigen, and viral RNA data for bamlanivimab, sotrovimab, and BRII 196/198, the first three investigational agents in TICO.

Antibody, antigen, and viral RNA levels are determined centrally, and may not be available at interim analyses. If data are available, key analyses will be included in interim reports.

### 12.1 Associations of Baseline Levels with Clinical Outcomes

For each treatment group, associations of baseline antibody status (negative versus positive), levels of plasma antigen, and levels of viral RNA at study entry, with time to *sustained recovery* through day 90 (primary efficacy outcome) and with important safety outcomes will be assessed.

### 12.2 Plasma Antigen Levels Through Day 5

Plasma antigen levels over time (Baseline, Days 1, 3, and 5) will be described using the following summary statistics, by treatment group, for all participants with follow-up data, and separately for participants who were nAb negative versus nAb positive at study entry:

- Number and percent of participants with antigen levels < 3 ng/L (“antigen negative”), and number and percent of participants with antigen levels < median antigen levels at

- study entry (the cut-point used for subgroup analyses).
- Side-by-side box plots of antigen levels. Antigen levels  $< 3 \text{ ng/L}$  (the lower limit of quantification) will be imputed as 2.9, and antigen levels will be plotted on the  $\log_{10}$ -scale.
- Geometric mean concentrations (GMC) of the antigen levels

**Hypothesis 1:** Over the first 5 days, antigen levels will decline faster in those receiving the investigational agent compared to those receiving placebo.

**Hypothesis 2:** The treatment effect (investigational agent versus placebo) on the antigen levels is stronger among participants who are nAb negative at study entry compared with those who are nAb positive at study entry.

To address these hypotheses, treatment groups will be compared for the percentage of participants who are antigen negative (i.e., antigen levels  $< 3 \text{ ng/L}$ ) at Days 1, 3, and 5, overall (Hypothesis 1) and within subgroups (Hypothesis 2).

- At each time point, the treatment difference will be estimated using a logistic regression model with the  $\log_{10}$ -transformed baseline antigen level and disease severity indicator as covariates, and ORs with 95% CIs and p-values will be cited.
- In addition to the treatment comparisons at each time point (Days 1, 3, and 5), longitudinal GEE models will be fitted for the proportion of participants who are antigen negative over time, and slopes over time will be compared between treatment groups. The GEE models will be adjusted for baseline levels and disease severity.
- In addition to estimating the treatment differences within each subgroup, heterogeneity of the treatment effect across subgroups by baseline nAb status (Hypothesis 2) will be assessed by testing for an interaction between the treatment group indicator and the subgroup indicator for baseline nAb status in an expanded GEE model.
- Unadjusted analysis will also be performed, as sensitivity analysis.

**Comment:** Within the full study population, treatment comparison will be adjusted for nAb status at study entry by including the nAb status and disease severity indicators as covariates. Within nAb subgroups, comparisons will be adjusted for disease severity.

As secondary analyses, treatment groups will also be compared for the percentage of participants with antigen levels  $<$  median antigen level at study entry, as well as for the geometric mean concentration (GMC) of antigen levels.

In order to compare treatment groups for geometric mean concentration (GMC) of antigen levels, antigen levels  $< 3 \text{ ng/L}$  will be imputed as 2.9 ng/L, and the treatment difference will be estimated as the GMC ratio for the investigational agent versus placebo. For this analysis, plasma antigen levels will be  $\log_{10}$ -transformed, mean differences will be estimated with 95% CIs in ANCOVA models that include the treatment indicator as fixed effect and the baseline  $\log_{10}$  antigen level and disease severity indicator as covariates, and the treatment difference will be back-transformed to the original scale to estimate the GMC ratio. These analyses will be performed in the full study population, as well as within subgroups by nAb status. Heterogeneity of the treatment effect across subgroups will be assessed by testing for an interaction between treatment group and subgroup indicator in expanded ANCOVA models for the  $\log_{10}$ -transformed antigen levels.

## 12.3 Antibody Levels Through Day 5

Levels of nAb and anti-N antibodies at baseline, Days 1, 3, and 5 will be described using the following summary statistics, by treatment group, for all participants with follow-up data, and separately within subgroups by antibody status (positive versus negative) at study entry. To investigate nAb levels over time, subgroups will be formed by nAb status. To investigate anti-N antibody levels over time, subgroups will be formed by anti-N antibody status. Similar analyses will be performed for anti-Spike IgG antibody levels.

- Number and percent of participants with nAb percent binding ratio  $\geq 30\%$  (“nAb positive”)
- Number and percent of participants with anti-N Ab specimen ratio  $\geq 1$  (“anti-N antibody positive”)
- Number and percent of participants with anti-Spike IgG antibody level  $\geq 770$  ng/mL (“anti-Spike IgG positive”)
- Side-by-side box plots of nAb, anti-N, and anti-Spike IgG antibody levels over time
- Median concentrations of the nAb, anti-N, and anti-Spike IgG antibody levels

**Comment:** The manufacturer of the anti-N antibody assay (BioRad) considers samples with specimen ratios  $< 0.8$  as “antibody negative”, and samples with values between 0.8 and 1 as “equivocal”. For our analyses, we refer to all samples with specimen ratio  $< 1$  as “anti-N negative”.

Treatment groups will be compared for the following outcomes, overall and within subgroups by antibody status at study entry:

- The percentage of participants who are nAb positive (i.e., percent binding ratio  $\geq 30\%$ ) at Days 1, 3, and 5, overall and within subgroups by nAb status at study entry.
- The percentage of participants who are anti-N antibody positive (i.e., specimen ratio  $\geq 1$ ) at Days 1, 3, and 5, overall and within subgroups by anti-N antibody status at study entry.
- The percentage of participants who are anti-Spike IgG antibody positive (i.e., antibody level  $\geq 770$  ng/mL) at study entry at Days 1, 3, and 5, overall and within subgroups by anti-Spike IgG antibody levels at study entry.

Statistical methods are similar to those described for comparing antigen levels over time.

In addition, at Days 1, 3, and 5, treatment groups will be compared for mean antibody levels (nAb, anti-N, and anti-Spike IgG levels), and the mean difference (investigational agent minus placebo) will be estimated with 95% CIs, overall and in subgroups by antibody status, using ANCOVA models that include the treatment indicator as fixed effect, and the baseline antibody level (continuous covariate) and disease severity indicator as covariates. Treatment groups will also be compared for mean change over time using longitudinal mixed effects models, comparing slopes of mean antibody levels over time between treatment groups. Heterogeneity of the treatment effect across subgroups will be assessed by testing for an interaction between treatment group and subgroup indicator in expanded longitudinal mixed effects models.

**Comment:** The analyses of mean levels of nAb and anti-N antibody levels are exploratory, as the assays are qualitative. In contrast, the anti-Spike IgG antibody assay is semi-quantitative, and for that assay percentiles will be considered in subgroup analyses as well as classification of results as antibody negative/positive.

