### Plasma Antigen Levels

SARS-CoV-2 nucleocapsid antigen levels were determined in 90  $\mu$ L plasma in duplicate using

a **Quanterix** assay (Simoa® SARS-CoV-2 N Protein Advantage, Quanterix, Bellerica, MA, USA). The lower limit of quantification for the assay is 3 ng/L.

- Antigen levels < 3 ng/L are considered “antigen negative”.

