**Comments:**

- When analyzed as continuous variable, Quanterix antigen levels <3 will be set to 2.9 ng/L.
- When analyzed as continuous variable, antigen levels will be  $\log_{10}$ -transformed.

**SARS-CoV-2 Viral RNA** was assessed at baseline from mid-turbinate nasal swabs.

Qualitative and quantitative assessments of the SARS-CoV-2 RNA in viral transport media (proxy for viral load) by RT-PCR were made centrally by ABML.

- *Qualitative RT-PCR analysis:* Extraction, master mix preparation, and RT-PCR were performed as described in the CDC 2019-Novel Coronavirus Real-Time RT-PCR Diagnostic Panel. RT-PCR was performed on an Applied Biosystems QuantStudio 7 Flex. Ct scores <40 for both nCoV N1 and nCoV N2 probe sets are scored as positive for the presence of SARS-CoV-2 RNA.
- *Quantitative RT-PCR analysis:* Quantitative RT-PCR analysis of the samples used the same RNA extracts prepared for the qualitative assay. Assay conditions were the same as outlined in the CDC protocol except the RNaseP probe was not used.

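### Setting antigen below 3 ng/L to 2.9 ng/L pulls the secondary GMC ratio toward 1 when the agent works, and can distort its nAb interaction; the main antigen tests are not affected

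*SAP*

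**What the plan says.** Appendix F of the SAP gives the assay limit: "The lower limit of quantification for the assay is 3 ng/L". Its comments add a general rule: "When analyzed as continuous variable, Quanterix antigen levels <3 will be set to 2.9 ng/L". Section 12.2 applies the rule to the geometric mean concentration (GMC). Values below the limit "will be imputed as 2.9 ng/L, and the treatment difference will be estimated as the GMC ratio for the investigational agent versus placebo". On the log10 scale, "mean differences will be estimated with 95% CIs in ANCOVA models that include the treatment indicator as fixed effect", with baseline log10 antigen and disease severity as covariates. The comparison is made in the full population and within nAb subgroups, and heterogeneity is assessed by "testing for an interaction between treatment group and subgroup indicator in expanded ANCOVA models".

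Section 12.2 also ranks the analyses. Hypothesis 1 reads: "Over the first 5 days, antigen levels will decline faster in those receiving the investigational agent compared to those receiving placebo". Hypothesis 2 says that this effect is stronger in nAb-negative participants. The analysis named for both is binary: "To address these hypotheses, treatment groups will be compared for the percentage of participants who are antigen negative" at Days 1, 3 and 5, by logistic regression and GEE, with the Hypothesis 2 interaction tested in an expanded GEE model. The GMC ratio comes afterwards, in the sentence that begins "As secondary analyses, treatment groups will also be compared for the percentage of participants with antigen levels".

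**The concern.** A value below 3 ng/L is known only to lie somewhere under the limit. Replacing all such values by one number just beneath it, and then treating that number as measured, removes any further fall. An agent that clears antigen faster has more values there, so its mean is raised by more than the placebo mean and the GMC ratio is drawn toward 1. The effect grows as antigen clears.

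The amount of shrinkage depends on the share of values below the limit. If that share differs between nAb-negative and nAb-positive participants, equal true ratios will be shrunk by different amounts, and the ANCOVA interaction will show a difference that the substitution created.

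At stake is the one planned treatment comparison of how far antigen falls. The other comparisons in section 12.2 cut the scale at 3 ng/L or at the baseline median.

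**Working it through.** The SAP gives no effect size, SD or expected share below the limit for antigen, so there is no figure of its own to reproduce. The check asks how far the rule moves a known ratio.

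**From the SAP:** limit 3 ng/L and substitute 2.9 ng/L (section 12.2, Appendix F); baseline median about 1000 ng/L in the bamlanivimab trial (section 9.2); for the simulation, 1417 infused participants in the AZD7442 trial, about 708 per arm, and 616 nAb-negative and 657 nAb-positive participants, about 308 and 328 per arm (Table E-1).

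**Assumed:** normal log10 antigen with SD 1 (range 0.8 to 1.2), a true GMC ratio of 0.50, and a range of placebo medians at follow-up.

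**Formula.** Let L = log10(3) = 0.4771 and S = log10(2.9) = 0.4624. For mean μ and SD σ, with a = (L − μ)/σ, the expected mean after substitution is

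M(μ) = S·Φ(a) + μ·(1 − Φ(a)) + σ·φ(a).

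The expected ratio is 10^(M(μ₁) − M(μ₀)), where μ₁ = μ₀ + log10(0.5) = μ₀ − 0.3010.

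**One case in full, placebo median 10 ng/L, σ = 1.**
- Placebo: μ₀ = 1, a = −0.5229, Φ = 0.3005, φ = 0.3480. M = 0.13896 + 0.69947 + 0.34797 = 1.1864.
- Active: μ₁ = 0.6990, a = −0.2218, Φ = 0.4122, φ = 0.3892. M = 0.19061 + 0.41084 + 0.38924 = 0.9907.
- Difference −0.1957, so the ratio is 10^(−0.1957) = 0.64 instead of 0.50.

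| Placebo median (ng/L) | Placebo below 3 | Active below 3 | Expected ratio (true 0.50) |
|---|---|---|---|
| 1000 | 0.6% | 1.3% | 0.503 |
| 300 | 2.3% | 4.5% | 0.51 |
| 100 | 6.4% | 11.1% | 0.53 |
| 32 | 15% | 24% | 0.57 |
| 10 | 30% | 41% | 0.64 |
| 3.2 | 49% | 61% | 0.73 |

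Changing the SD to 0.8 or 1.2 gives 0.515 to 0.545 at a median of 100 and 0.62 to 0.65 at 10. With a true ratio of 0.70, the estimate is 0.702 at 1000 and 0.785 at 10.

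**Simulation with the baseline covariate** (708 per arm, assumed correlation 0.7 between baseline and follow-up, 200 replicates per case):
- True ratio 0.50: ANCOVA after substitution gave 0.508, 0.529, 0.573, 0.634 and 0.737 at placebo medians of 300, 100, 30, 10 and 3, close to the formula. Coverage of the nominal 95% interval was 95%, 92%, 58%, 5% and 0%. Tobit regression gave 0.496 to 0.504 throughout.
- True ratio 1: estimates were 0.99 to 1.01 and rejection was between 2% and 6%, so there is no bias and no inflation of type I error.

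**Interaction.** Give both nAb subgroups the same true ratio of 0.60, and assume follow-up medians of 300 ng/L (nAb-negative) and 10 ng/L (nAb-positive). The formula gives 0.61 and 0.71; simulation gives 0.62 and 0.71, against 0.61 and 0.60 by Tobit. The apparent difference points in the direction of Hypothesis 2. With an nAb-positive median of 30 the simulated figure is 0.66 instead of 0.71.

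**The case against.** A reader might infer that the tests of Hypotheses 1 and 2 are themselves compromised. Section 12.2 does not support that. The analysis named for both hypotheses classifies each participant as below 3 ng/L or not, and this outcome is the same whatever number is assigned under the limit. The interaction labelled as the Hypothesis 2 test is in the GEE model for that binary outcome. Only the additional ANCOVA interaction uses substituted outcomes. This part of the objection stands in full.

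The size can also be disputed. The only antigen level in the SAP is a baseline median of about 1000 ng/L, where the expected ratio is 0.503. The larger figures need medians of about 30 ng/L or less within five days. The subgroup medians behind the interaction example are assumed. This stands too: the size is conditional on a share that the SAP does not give.

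The SAP has partial safeguards. Section 12.2 already calls for the percentage below 3 ng/L by arm and nAb status over time, so the extent of the problem will be visible. Section 3 makes ANCOVA conditional on its assumptions and allows rank-based or quantile methods. That fallback is optional, is triggered by skewness, and does not mention values below a quantification limit.

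Finally, Tobit regression has its own assumption. If some participants have truly cleared antigen, there is a mass of values at zero instead of a lognormal tail, and Tobit extrapolates. With a placebo median of 100, a ratio of 0.50 among those still positive, and assumed true clearance of 20% on placebo and 30% on active, substitution gives about 0.45 and Tobit about 0.32. In that example 0.50 is not the overall effect, because it leaves out the extra clearance on the agent. The example shows that the answer depends on the model. That is a reason to report both analyses, not a reason to keep substitution alone.

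**Conclusion.** The point holds for the secondary GMC ratio and its ANCOVA interaction, and for nothing beyond them. When the agent lowers antigen, the 2.9 rule pulls the ratio toward 1. Under a true ratio of 0.50 and an SD of 1, the shift is about 0.03 or less while roughly 6% or fewer of placebo values are below the limit, 0.07 at 15%, 0.14 at 30% and 0.23 at 49%. True ratio, SD and share below the limit are all assumptions. The problem is most likely to matter at Day 5, and in whichever nAb subgroup has the lower antigen.

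Two stronger readings should be set aside. The rule does not create a false overall antigen effect: at a true ratio of 1 there is no bias. Nor do the documents show that the share below the limit differs by nAb status, so a distorted interaction is a plausible risk and not a demonstrated one. The primary endpoint is not involved. This is a worthwhile improvement of minor weight.

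**What to change.** In section 12.2, estimate the GMC ratio and its treatment-by-nAb interaction with a left-censored normal (Tobit) regression of log10 antigen, limit 3 ng/L, with the same covariates as the planned ANCOVA. Keep the 2.9 ng/L substitution for three uses: as a sensitivity analysis of the ratio, for the box plots, and for the baseline antigen covariate. Amend the comment in Appendix F to match. Show the already planned percentage below 3 ng/L, by arm, day and nAb subgroup, beside each ratio.

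The cost is a few sentences of SAP text and standard software; no new data are needed. The drawback is reliance on normality of log10 antigen below the limit, with extrapolation if some participants have truly cleared antigen. For that reason both results should be reported, and a material gap between them should be read as dependence on the model.
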